9.2.1 General Assessments

9.2.1.1 Informed Consent

All subjects must sign and personally date the IRB/IEC and Amgen approved informed consent before any study-specific procedures are performed.

9.2.1.2 Demographics

Demographic data collection including sex, age, race, and ethnicity will be collected in order to study their possible association with subject safety and treatment effectiveness. Additionally, demographic data will be used to study the impact on biomarkers variability and PK of the protocol-required therapies.

9.2.1.3 Medical History

The Investigator or designee will collect a relevant medical and surgical history that started within 5 years or as necessary for chronic or co-morbid conditions prior to enrollment through the start of the adverse event reporting period. Medical history will include information on the subject's concurrent medical conditions. Record all findings on the medical history CRF. In addition to the medical history above, SLE history must date back to the original diagnosis. The current toxicity grade will be collected for each condition that has not resolved.

9.2.1.4 Physical Examination

Physical examination will be performed as per standard of care. Physical examination findings should be recorded on the appropriate CRF (eg, medical history, event).

9.2.1.5 Physical Measurements

Weight in kilograms and height in centimeters should be measured without shoes.

9.2.1.6 Substance Abuse History

Obtain a detailed history of prior and/or concurrent use of alcohol and of nicotine or tobacco containing products.

9.2.2 Efficacy Assessments

9.2.2.1 Systemic Lupus Erythematosus Disease Activity Index-2000

The systemic lupus erythematosus disease activity index-2000 (SLEDAI-2K) is a global index that evaluates disease activity and includes 24 items collecting specific manifestations in 9 organ systems: neurological, musculoskeletal, renal, mucocutaneous, general, heart, respiratory, vascular, and hematological. The maximum score is 105.

A SLEDAI score will be used for eligibility purposes but the anti-dsDNA antibodies and serum complement will not count towards the total score. After screening, anti-dsDNA antibodies and serum complement will be counted toward the total SLEDAI-2K score.

Systemic lupus erythematosus disease activity index-2000 descriptors will be scored based on a review of medical history, physical examination, and clinical laboratory findings. Findings should reflect activity during the 10 days prior to the current visit.

9.2.3 Safety Assessments

Planned time points for all safety assessments are listed in the Schedule of Activities ([Table 2-1](#) and [Table 2-2](#)).

9.2.3.1 Adverse Events

9.2.3.1.1 Time Period and Frequency for Collecting and Reporting Safety Event Information

9.2.3.1.1.1 Disease-related Events

Disease-related events are defined in [Appendix 4](#).

The investigator is responsible for ensuring that all disease-related events observed by the investigator or reported by the subject that occur after the first dose of investigational product(s)/study treatment/protocol-required therapies through the safety follow-up visit are recorded using the Event CRF.

All serious disease-related events will be recorded and reported to the sponsor or designee within 24 hours. The investigator will submit any updated serious disease-related event data to the sponsor within 24 hours of it being available.

Disease-related events assessed by the investigator to be more severe than expected and/or related to the investigational product(s)/study treatment/protocol-required therapies, and determined to be serious, must be reported on the Event CRF as serious adverse events and recorded and reported per [Sections 9.2.3.1.1.3](#) and [Appendix 4](#).

Disease-related events pre-defined for this study include: lupus-related joint pain, joint stiffness, joint swelling, rash, alopecia, and mucosal ulcers.

9.2.3.1.1.2 Adverse Events

The adverse event grading scale to be used for this study will be the CTCAE and is described in [Appendix 4](#).

The investigator is responsible for ensuring that all adverse events observed by the investigator or reported by the subject that occur after first dose of investigational product through the safety follow-up visit are reported using the Event CRF.

9.2.3.1.1.3 Serious Adverse Events

The investigator is responsible for ensuring that all serious adverse events observed by the investigator or reported by the subject that occur after signing of the informed consent through safety follow-up visit are reported using the Event CRF.

All serious adverse events will be collected, recorded and reported to the sponsor or designee within 24 hours, as indicated in [Appendix 4](#). The investigator will submit any updated serious adverse event data to the sponsor within 24 hours of it being available.

The criteria for grade 4 in the CTCAE grading scale differs from the regulatory criteria for serious adverse events. It is left to the investigator's judgment to report these grade 4 abnormalities as serious adverse events.

9.2.3.1.1.4 Serious Adverse Events After the Protocol-required Reporting Period

There is no requirement to monitor study subjects for serious adverse events following the protocol-required reporting period or after end of study. However, these serious adverse events can be reported to Amgen. Per local requirements in some countries, investigators are required to report serious adverse events that they become aware of after end of study. If serious adverse events are reported, the investigator is to report them to Amgen within 24 hours following the investigator's knowledge of the event.

Serious adverse events reported outside of the protocol-required reporting period will be captured within the safety database as clinical trial cases and handled accordingly based on relationship to investigational product.

The method of recording, evaluating, and assessing causality of adverse events, disease-related events, and serious adverse events and the procedures for completing and transmitting serious adverse event reports are provided in [Appendix 4](#).

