3.2.1.3 Clinical Experience With Low Dose IL-2 in Systemic Lupus Erythematosus

Treatment with low dose IL-2 has been associated with clinical efficacy in 2 small clinical trials. In one recently reported study of 12 patients with moderate to severe SLE (Systemic Lupus Erythematosus Disease Activity Index [SLEDAI] score ≥ 6 despite treatment with 2 different immunosuppressive therapies), 10/12 subjects (83.3%) achieved a reduction in SELENA SLEDAI score and 8/12 (66.7%) achieved a clinical response after receiving four 5-day cycles of low dose IL-2 therapy separated by washout periods of 9 and 16 days. Clinical responses included complete resolution of SLE manifestations including rash, arthralgias, myositis and alopecia. Complement levels increased but no change in anti-double stranded DNA (anti-dsDNA) antibodies was observed. Regulatory T cells numbers increased in all treated subjects ([Humrich et al, 2016](#); [Humrich et al, 2015](#)). In a second study of 38 SLE patients who completed three 2-week cycles of low dose IL-2 over 12 weeks, 34/38 subjects (89.5%) achieved a Systemic Lupus Erythematosus Responder Index 4 (SRI-4) response at the end of 12 weeks, with concomitant decreases in anti-dsDNA antibodies and increase in complement levels. Regulatory T cells numbers increased in most treated subjects ([He et al, 2016](#)). In both studies low dose IL-2 was generally well- tolerated, though constitutional symptoms (eg, fever, myalgias, arthralgias, flu-like symptoms) were reported at the higher dose levels. Overall these studies provide compelling support for further investigation of low dose IL-2 for the treatment of SLE.

[figure not shown]
3.2.2 Amgen Investigational Product Background: AMG 592

AMG 592 is an Fc IL-2 mutein fusion protein with increased Treg selectivity compared to recombinant IL-2, which has been developed to preferentially expand Tregs in subjects with inflammatory diseases (refer to the Investigator's Brochure for more details).

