Appendix 3. Study Governance Considerations

Dose Level Review Meetings and Data Review Team

Dose Level Review Meetings

The study will employ Dose Level Review Meetings (DLRM). The DLRM team will be composed of the investigator(s), Amgen Medical Monitor, and Amgen Global Safety Officer or designee. Other optional Amgen representatives (eg, Amgen biostatistics representative, Clinical Trial Manager) may be included as appropriate. A quorum, defined as > 50% of the participating investigators who have enrolled at least 1 subject in the study or their qualified designee (ie, sub-investigator or research nurse or study coordinator possessing hard copy documentation [eg, email] of the investigator's vote regarding the dose level review), must be in attendance for the DLRM. The DLRM will be rescheduled if a quorum is not reached.

Voting members of the DLRM will include the Amgen medical monitor, the Amgen global safety officer or designated safety scientist, and all participating investigators or their qualified medical doctor designee(s). The majority opinion of the investigators will count as 1 vote; the medical monitor will cast 1 vote and the global safety officer will cast 1 vote. A majority positive vote indicating an acceptable safety profile for the investigational product is required to allow dose level escalation or modification and/or cohort continuation/expansion to proceed. All available study data including demographics, medical history, concomitant medications, adverse events, electrocardiograms, vital signs, laboratory results, and emerging pharmacokinetic and pharmacodynamics data will be reviewed. Data to be reviewed may be unqueried.

Study investigators will be informed of DLRM dosing decisions via email notification. Only in the following limited circumstances, dose decisions can be made by the Amgen Medical Monitor and Amgen Global Safety Officer without convening a DLRM:

- The Amgen Medical Monitor and Amgen Global Safety Officer may decide to begin the next cohort using a de-escalated dose (de-escalated from the dose level of the most recent cohort), if this de-escalated dose had been previously evaluated during a DLRM.

Approved

Regulatory and Ethical Considerations

This study will be conducted in accordance with the protocol and with:

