Any arrangements for compensation to subjects for injury or illness that arises in the study are described in the Compensation for Injury section of the Informed Consent that is available as a separate document.

Approved

Appendix 4. Safety Events: Definitions and Procedures for Recording, Evaluating, Follow-up and Reporting

Definition of Disease-related Event

Disease-related Event Definition

Disease-related events are events (serious or non-serious) anticipated to occur in the study population due to the underlying disease. See Section 9.2.3.1.1.1 for the list of disease-related events. All serious disease-related events will be recorded and reported to the sponsor or designee within 24 hours.
 
Disease-related events that would qualify as an adverse event or serious adverse event:
 
○ An event based on the underlying disease that is worse than expected as assessed by the investigator for the subject's condition or if the investigator believes there is a causal relationship between the investigational product(s)/study treatment/protocol-required therapies and disease worsening, this must be reported as an adverse event or serious adverse event. 
Disease-related events that do not qualify as adverse events or serious adverse events:
 
○ An event which is part of the normal course of disease under study (eg, disease progression in oncology or hospitalization due to disease progression) is to be reported as a disease-related event.

Definition of Adverse Event

Adverse Event Definition

An adverse event is any untoward medical occurrence in a clinical study subject irrespective of a causal relationship with the study treatment.
 
Note: An adverse event can therefore be any unfavorable and unintended sign (including an abnormal laboratory finding), symptom, or disease (new or exacerbated) temporally associated with the use of a treatment, combination product, medical device or procedure.

Events Meeting the Adverse Event Definition

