## **7. Planned Analyses**

### **7.1 DLRMs**

The study will have DLRMs for each cohort after the last subject in the cohort completes week 4 visit. Section 3.1 details the timings and scope of each DLRM planned for the study.

All available data the subjects up to and including the data snapshot date will be included in the analysis based on an “as-is” snapshot of the database without data locking. Data will be subject to ongoing checks for integrity, completeness and accuracy in accordance with the Data Management Plan; however, there is no requirement to resolve outstanding data issues ahead of the DLRM snapshot. DLRM analysis will include subject-level listings and plots of available safety data (labs, and vitals) for each

---

cohort and the BLRM analysis if required. The recommendations for dose escalation/dose modifications will be based on the DLRMs.

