### **9.6.2 Adverse Events**

The Medical Dictionary for Regulatory Activities (MedDRA) version 24.0 or later will be used to code all events categorized as adverse events, all disease-related events to a system organ class and a preferred term. The severity of each adverse event will be graded using CTCAE criteria version 4.03.

Subject incidence of all treatment-emergent, serious treatment-emergent, treatment-related, serious treatment-related, disease-related treatment-emergent, those leading to withdrawal from investigational product, and fatal adverse events will be tabulated by system organ class in alphabetical order, preferred term and grade in descending order of frequency. Subject incidence of treatment-emergent adverse events identified by

COVID-19 standardized MedDRA queries and serious adverse events occurring on or after the COVID-19 infection will also be summarized.

Subject incidence of treatment-emergent events of interest (standardized MedDRA queries and/or Amgen Medical Queries) will also be summarized according to their categories, preferred term, and worst severity grade. Events of interest could include but are not limited to Hypersensitivity, Tachyarrhythmias, Tachypnea, Hematopoietic Cytopenia, Drug Reaction with Eosinophilia, Leucocyte Changes, Infection and Infestation, Cytokine Release Syndrome, and Injection Site Reaction. Number of episodes and duration of treatment-emergent injection site reactions will be further summarized by treatment group.

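### Lupus-related joint symptoms are split between adverse event and disease-related tables by blinded attribution, and no combined count per subject is planned

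*Protocol*

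**What the plan says.** **Classification.** Protocol 9.2.3.1.1.1 states: "Disease-related events pre-defined for this study include: lupus-related joint pain, joint stiffness, joint swelling, rash, alopecia, and mucosal ulcers". These are recorded on the Event CRF, the same form as adverse events, from the first dose to the safety follow-up visit. Appendix 4 first defines adverse events without regard to cause: "An adverse event is any untoward medical occurrence in a clinical study subject irrespective of a causal relationship with the study treatment". It then has a category headed "Disease-related events that do not qualify as adverse events or serious adverse events", for events in the normal course of the disease. Such an event moves to the adverse events if it is worse than expected for that subject, or "if the investigator believes there is a causal relationship between the investigational product(s)/study treatment/protocol-required therapies and disease worsening".

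**Background.** On the two lupus studies of low-dose IL-2, Protocol 3.2.1.3 says treatment was generally well tolerated, "though constitutional symptoms (eg, fever, myalgias, arthralgias, flu-like symptoms) were reported at the higher dose levels". Protocol 3.2.1.2 lists arthralgia among the grade 1 symptoms seen with aldesleukin in a chronic graft-versus-host disease trial.

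**Analysis.** The endpoint tables (Protocol 4.1, SAP 2.1) list treatment-emergent adverse events and do not mention disease-related events. SAP 9.6.1 does include disease-related events in the primary safety analysis. Protocol 10.3.2.3.2 tabulates them by system organ class and preferred term. SAP 9.6.2 gives them their own tabulation, also by grade: "disease-related treatment-emergent, those leading to withdrawal from investigational product, and fatal adverse events will be tabulated by system organ class". SAP 9.1 summarizes data by treatment. SAP 5.4 defines a treatment-related adverse event as a subset of treatment-emergent adverse events.

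**Dose review.** Protocol Appendix 3 gives the scope as "All available study data including demographics, medical history, concomitant medications, adverse events, electrocardiograms, vital signs, laboratory results" and emerging PK and PD data. SAP 7.1 says "DLRM analysis will include subject-level listings and plots of available safety data (labs, and vitals) for each" cohort. Neither names disease-related events.

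**The concern.** Joint pain is on the disease-related list, and arthralgia is a symptom that the protocol's own background ties to IL-2, the cytokine from which AMG 592 is engineered. For one lupus patient with joint pain, a blinded investigator must decide whether it is the usual disease, worse than usual, or drug. That decision determines which table the event enters. The joint-symptom count in the treatment-emergent table therefore depends partly on individual attribution, although the general definition of an adverse event avoids attribution.

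What is at stake is a dose-related rise in joint symptoms that is spread thinly over two tables, each of which looks unremarkable. Rash is a secondary case. Hypersensitivity is a named event of interest in SAP 9.6.2, Protocol 3.3 reports two serious hypersensitivity reactions to AMG 592 (none in this study), and lupus rash is on the disease-related list.

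**Working it through.** **1. Where a drug-caused joint symptom can appear.**

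| Output | Filed as adverse event | Filed as disease-related |
|---|---|---|
| Treatment-emergent table (SAP 5.4, 9.6.2) | yes | no |
| Treatment-related table (SAP 5.4, 9.6.2) | yes, if judged related | no, because it must first be a treatment-emergent adverse event |
| Disease-related table (Protocol 10.3.2.3.2, SAP 9.6.2) | no | yes |
| Events-of-interest searches (SAP 9.6.2) | yes | not stated |
| Combined count, each subject once per term | not planned | not planned |

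**2. Subject incidence does not add.** A subject may have one episode filed each way. If a of n subjects are in the adverse event row and b of n in the disease-related row, the number of distinct subjects d satisfies max(a, b) ≤ d ≤ min(n, a + b). With n = 5 and a = b = 2 (an example), d lies between 2 and 4, that is 40% to 80%. The two tables cannot say which. The same holds for the worst grade per subject.

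**3. The plan's own figures.** Protocol 10.1 and SAP 3.2 give the chance of at least one event, 1 − (1 − p)^n.
- n = 5, p = 25%: 1 − 0.75^5 = 76.3%; the plan says 76%.
- n = 5, p = 20%: 1 − 0.80^5 = 67.2%; the plan says 67%.
- n = 21, p = 1%: 1 − 0.99^21 = 19.0%; the plan says 19%.
- n = 21, p = 5%: 1 − 0.95^21 = 65.9%; the plan says 66%.

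All four reproduce.

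**4. Illustration for the adverse event table read alone.** Let q be the share of drug-caused cases filed as disease-related. The documents give no value, so q is assumed and shown over a range, with filing treated as independent between subjects. The chance of at least one event in that table is 1 − (1 − p(1 − q))^n.

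| q (assumed) | n = 5, p = 25% | n = 21, p = 5% |
|---|---|---|
| 0 | 76% | 66% |
| 0.25 | 65% | 55% |
| 0.50 | 49% | 41% |
| 0.75 | 28% | 23% |

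For example, at q = 0.50 with n = 5: p(1 − q) = 0.125 and 1 − 0.875^5 = 48.7%. If the adverse event and disease-related rows are read together, every entry returns to the q = 0 row, because the events are also collected and tabulated.

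**5. Grade.** Appendix 4 places the duty to assess severity on adverse events and serious adverse events. It does not name disease-related events, yet SAP 9.6.2 tabulates them by grade. A combined table by worst grade relies on that grade being recorded.

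**The case against.** A reader might infer that the primary analysis can miss a joint-symptom signal. The documents do not support that. SAP 9.6.1 places disease-related events inside the primary safety analysis, and they are coded, tabulated by preferred term and grade, and summarized by treatment. An imbalance against placebo could be seen in that table.

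A reader might also extend the overlap to the whole list. Arthralgia is attributed to aldesleukin or low-dose IL-2, not to AMG 592, which the protocol describes as more selective for regulatory T cells. Nothing in the documents ties mucosal ulcers or alopecia to either drug. The erythema in Protocol 3.3 is at or near the injection site. Fever, malaise, myalgia and flu-like symptoms are not on the list and stay among the adverse events.

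Three further points count against a strong claim.
- The list says lupus-related joint pain, so joint pain not attributed to lupus is an ordinary adverse event. Appendix 4 also counts exacerbation of a pre-existing condition as an adverse event, though it does not say how this fits with the disease-related rule.
- The dose-review scope of all available study data already covers disease-related events. The laboratory and vital-signs wording in SAP 7.1 names no adverse events either, so it shows no gap specific to these events.
- No document says how often, or in which direction, investigators would misfile.

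All of this stands. What remains is that two separate incidence tables do not give one count of subjects, and that the split between them follows attribution.

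**Conclusion.** The point holds as a reporting weakness, essentially for joint pain, stiffness and swelling, with rash second. A drug-caused rise would be divided by blinded attribution. The part left as disease-related would be outside the treatment-related table, and the number of distinct subjects per term could not be recovered from the planned tables. No data are lost, and no sample-size figure or formal test is affected (SAP 2.2 plans no hypothesis test).

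The size is unknown. The fall from 76% to between 65% and 28% rests on an assumed q of 0.25 to 0.75, applies only to the adverse event table read alone, and should not be quoted as an estimate. A combined table is a cheap improvement. It gives the placebo comparison free of attribution that randomization makes possible, although with about 8 placebo subjects in all it will remain descriptive.

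**What to change.** In SAP 9.6.2, add one table of subject incidence of treatment-emergent adverse events and disease-related events combined, by preferred term, worst grade and treatment group with placebo alongside, counting each subject once per term. State that the events-of-interest searches, for example Hypersensitivity, run on this combined set. Keep the existing separate tables.

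Before programming, check that disease-related events carry a grade on the Event CRF, and that the same symptom receives the same preferred term in both classes. If it does not, define the grouping in the SAP.

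Two wording points are secondary. Align the endpoint tables in Protocol 4.1 and SAP 2.1 with SAP 9.6.1, and name disease-related events in the dose-review data lists (Protocol Appendix 3, SAP 7.1 and 9.1).

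The cost is one extra table and a few sentences; the events are already collected. The downside is that background lupus symptoms raise the combined incidence in every group, so the table should be read as a comparison with placebo and not as a rate of drug toxicity.
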